7.24 Safety-related Study Stopping Rules

If any patient experiences a life-threatening (Grade 4) adverse event or death which is considered by the sponsor to be possibly, probably, or definitely related to study drug **or the IDDD**, or if 2 or more patients experience a Grade 3 adverse event during the trial that is considered by the sponsor to be possibly, probably, or definitely related to the study drug **or the IDDD**, then the site will be instructed to halt further HGT-1410 administration to all patients and the safety data reviewed. Following a review of safety data, the study will be either:

- Resumed unchanged
- Resumed with modifications to the protocol or
- Terminated

Patient safety will be monitored on a continuous basis during this study until the last patient completes his or her last scheduled study visit/assessment.

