10.6 Efficacy, Safety, and Pharmacodynamic Evaluations

10.6.1 Primary Analyses

10.6.1.1 Safety Analysis

In general, safety assessments will be based on all assessments post-baseline. The assessment of safety will be based primarily on the frequency of AEs, and on the frequency of clinically notable abnormal vital sign and laboratory values. Changes from baseline will be calculated by subtracting the baseline value from the post-baseline value.

All enrolled patients who had an IDDD surgical procedure and/or received administration of HGT-1410 will be included in the safety analysis.

Adverse events will be recorded throughout the study and at early termination. Adverse events and medical conditions will be coded using the Medical Dictionary for Regulatory Activities (MedDRA).

Adverse events will be summarized by presenting, for each dose group, the number and percentage of patients having any AE, having an AE in system organ class, and having each individual AE. In addition, those events which resulted in death or were otherwise classified as serious will be presented in a separate listing. The incidence of treatment-emergent adverse events, defined as all AEs from the time of the surgery for IDDD implantation to the last follow up contact, ie, 30 days after the last HGT-1410 administration, (new or worsened from baseline) will be summarized by system organ class, severity, type of adverse event and relationship to trial medication/procedure.

Treatment-emergent AEs deemed related to HGT-1410 administration will be summarized separately.

IDDD and procedure-related AEs will be summarized within system organ class by preferred term. IDDD and procedure-related AEs will be tabulated by severity (mild, moderate, severe) and degree of relatedness. Separate tabulations will be provided for adverse events related to the IDDD, device surgical procedure (including post-implant infections) and IT administration process. These summaries will be presented by device and overall, as appropriate.

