Fibrosis-cosmesis	Fibrosis-cosmesis	Visible only on close examination	Readily apparent but not disfiguring	Significant disfigurement; operative intervention indicated if patient chooses	—	—

MUSCULOSKELETAL/SOFT TISSUE

Page 2 of 4

		Grade				
Adverse Event	Short Name	1	2	3	4	5
Fibrosis-deep connective tissue	Fibrosis-deep connective tissue	Increased density, "spongy" feel	Increased density with firmness or tethering	Increased density with fixation of tissue; operative intervention indicated; interfering with ADL	Life-threatening; disabling; loss of limb; interfering with vital organ function	Death
ALSO CONSIDER: Induration/fibrosis (skin and subcutaneous tissue); Muscle weakness, generalized or specific area (not due to neuropathy) – Select ; Neuropathy: motor; Neuropathy: sensory.						
Fracture	Fracture	Asymptomatic, radiographic findings only (e.g., asymptomatic rib fracture on plain x-ray, pelvic insufficiency fracture on MRI, etc.)	Symptomatic but non-displaced; immobilization indicated	Symptomatic and displaced or open wound with bone exposure; operative intervention indicated	Disabling; amputation indicated	Death
Joint-effusion	Joint-effusion	Asymptomatic, clinical or radiographic findings only	Symptomatic; interfering with function but not interfering with ADL	Symptomatic and interfering with ADL	Disabling	Death
ALSO CONSIDER: Arthritis (non-septic).						
Joint-function ⁵	Joint-function	Stiffness interfering with athletic activity; ≤25% loss of range of motion (ROM)	Stiffness interfering with function but not interfering with ADL; >25 – 50% decrease in ROM	Stiffness interfering with ADL; >50 – 75% decrease in ROM	Fixed or non-functional joint (arthrodesis); >75% decrease in ROM	—
ALSO CONSIDER: Arthritis (non-septic).						
Local complication – device/prosthesis-related	Device/prosthesis	Asymptomatic	Symptomatic, but not interfering with ADL; local wound care; medical intervention indicated	Symptomatic, interfering with ADL; operative intervention indicated (e.g., hardware/device replacement or removal, reconstruction)	Life-threatening; disabling; loss of limb or organ	Death
Lumbar spine-range of motion	Lumbar spine ROM	Stiffness and difficulty bending to the floor to pick up a very light object but able to do activity	Some lumbar spine flexion but requires a reaching aid to pick up a very light object from the floor	Ankylosed/fused over multiple segments with no L-spine flexion (i.e., unable to reach to floor to pick up a very light	—	—

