7.2 Physical Examination

A full physical examination or a symptom-directed physical examination of each patient will be performed at time points detailed in [Appendix 1](#) Schedule of Events.

Any changes from the screening physical examination will be captured as AEs in the eCRF. If the patient experiences an AE associated with genitourinary evaluation, the patient may have the genitourinary evaluation performed by their primary care provider and a follow-up report will be sent to the investigator. Therefore, the genitourinary evaluation may not need to be performed again if the examination occurred within the visit window for that time point.

Note: if the patient's hearing cannot be assessed during the physical examination, the patient will have an Ears, Nose, and Throat Evaluation performed under anesthesia at the screening/start of study visit. If it is determined that the patient requires pressure-equalization (PE) tubes, they may be implanted during that evaluation (see Section 7.9). Note: PE tubes may be re-implanted if they fall out during this study.

The physical examination findings will be recorded on the eCRF and will include a review of the patient's general appearance as well as the following evaluations:

- Head and neck
- Eyes, ears, nose, and throat
- Chest and lungs
- Cardiovascular
- Abdomen
- Skin
- Lymphatic
- Musculoskeletal
- Neurological (symptom directed and at least every 12 months)
- Endocrine
- Genitourinary (as per referring physician)

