7.22 Adverse Events

7.22.1 Definitions of Adverse Events and Serious Adverse Events

7.22.1.1 Adverse Event

An AE is any noxious, pathologic, or unintended change in anatomical, physiologic, or metabolic function as indicated by physical signs, symptoms, or laboratory changes occurring in any phase of a clinical study, whether or not considered study drug-related. This includes an exacerbation of a pre-existing condition. Once the informed consent is signed and dated, any adverse event prior to the start of study drug must be reported.

AEs include:

- Worsening (change in nature, severity, or frequency) of conditions present at the onset of the study
- Intercurrent illnesses
- Drug interactions
- Events related to or possibly related to concomitant medications
- Abnormal laboratory values (this includes significant shifts from baseline within the range of normal that the investigator considers to be clinically important)
- Clinically significant abnormalities in physical examination, vital signs, and weight

Throughout the study, the investigator must record all AEs on the AE eCRF, regardless of the severity or relationship to study drug. The investigator should treat patients with AEs appropriately and observe them at suitable intervals until the events stabilize or resolve. AEs may be discovered through observation or examination of the patient, questioning of the patient, complaint by the patient, or by abnormal clinical laboratory values.

In addition, AEs may also include laboratory values that become significantly out of range. In the event of an out-of-range value, the laboratory test should be repeated until it returns to normal or can be explained and the patient's safety is not at risk.

All AEs should be recorded with causality assessment.

The information presented below is intended to provide issues to consider for AEs associated with intrathecal injections of HGT-1410. In general, these AEs can be classified as follows:

- Adverse events due to systemic exposure to HGT-1410 caused by the drug diffusion from the CSF to the peripheral circulation;
 - Adverse events related to the direct delivery of HGT-1410 to the intrathecal CSF space and meninges, and subsequent diffusion into brain parenchyma, via an intrathecal route
 - IDDD-related AEs
-

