7.22.1.2 Potential Adverse Events: Intrathecal recombinant human heparan N-sulfatase

ADVERSE EVENTS RELATED TO THE DIRECT DELIVERY OF HGT-1410 TO THE CNS THROUGH INTRATHECAL ADMINISTRATION

Examples of AEs observed in other published clinical trials with intrathecally-administered peptides or proteins, include, but are not limited to the following: headache, fever, feeling of warmth, sensory paresthesias (including feelings of warmth, tingling, or pain) or autonomic symptoms such as dry mouth or gustatory abnormalities (including loss of smell and metallic taste). Changes in mental cognitive status or level of consciousness that are not caused by pre-medication may either occur acutely or develop post-injection, over time

ADVERSE EVENTS DUE TO SYSTEMIC EXPOSURE TO HGT-1410

Although HGT-1410 is given intrathecally only, some proportion of the drug will diffuse from the CSF into the peripheral circulation. The resulting systemic exposure may cause events that are typically seen in patients receiving ERT via an intravenous administration, known as infusion-related reactions. An infusion-related reaction is defined as an adverse event that (1) begins either during or within 24 hours after the start of the infusion, and (2) is judged as possibly or probably related to study drug. Other AEs that occur prior to the infusion, along with AEs associated with protocol-defined testing and assessments (laboratory testing and physical examinations) that were performed prior to the infusion will not be defined as infusion-related reactions.

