7.22.3 Classification of Adverse Events and Serious Adverse Events

The National Cancer Institute Common Terminology Criteria for Adverse Events (NCI CTCAE) version 3.0 grading scale should be referenced when assessing the severity of an AE (see [Appendix 6](#)). If an AE is not described in the NCI CTC, the severity should be recorded based on the scale provided in Table 7-3. The severity of all AEs/SAEs should be recorded on the appropriate eCRF page. Adverse events are graded as Grade 1, 2, 3, 4, or 5 corresponding, respectively, to a severity of mild, moderate, severe, life-threatening, or death.

Table 7-3 Adverse Event Severity

Severity	Definition
Grade 1 (Mild)	No limitation of usual activities.
Grade 2 (Moderate)	Some limitation of usual activities.
Grade 3 (Severe)	Inability to carry out usual activities.
Grade 4 (Life-threatening)	Immediate risk of death.
Grade 5 (Death related to an AE)	Death

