7.22.4 Relatedness of Adverse Events and Serious Adverse Events

Relationship of an AE or SAE to investigational product, device, device surgical procedure, or IT administration process is to be determined by the investigator based on the definitions in Table 7-4:

Table 7-4 Adverse Event Relatedness

Relationship to Product(s)	Definition
Not Related	Unrelated to study drug, device, device surgical procedure, or IT administration process.
Possibly Related	A clinical event or laboratory abnormality with a reasonable time sequence to administration of study drug, device, device surgical procedure, or IT administration process but which could also be explained by concurrent disease or other drugs or chemicals.

Table 7-4 Adverse Event Relatedness

Relationship to Product(s)	Definition
Probably Related	A clinical event or laboratory abnormality with a reasonable time sequence to administration of study drug, device, device surgical procedure, or IT administration process unlikely to be attributable to concurrent disease or other drugs and chemicals and which follows a clinically reasonable response on de-challenge. The association of the clinical event or laboratory abnormality must also have some biologic plausibility, at least on theoretical grounds.
Definitely Related	The event follows a reasonable temporal sequence from administration of the medication, device, device surgical procedure, or IT administration process follows a known or suspected response pattern to the medication, is confirmed by improvement upon stopping the medication (dechallenge) and reappears upon repeated exposure (rechallenge). Note that this is not to be construed as requiring re-exposure of the patient to study drug; however, the determination of definitely related can only be used when recurrence of event is observed.

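### The device and procedure AE severity table has no place for Grades 4 and 5, and Section 7.2 records examination changes as AEs that the AE definition would not

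*Protocol*

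**What the plan says.** **Severity of device events.** Section 10.6.1.1, under the primary safety analysis, states: "IDDD and procedure-related AEs will be tabulated by severity (mild, moderate, severe) and degree of relatedness". Separate tabulations follow for events related to the device, to the device surgery and to the intrathecal administration process, shown by device and overall. Section 7.22.3 sets the scale for all events: "Adverse events are graded as Grade 1, 2, 3, 4, or 5 corresponding, respectively, to a severity of mild, moderate, severe, life-threatening, or death".

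**Physical examination.** Section 7.2 states: "Any changes from the screening physical examination will be captured as AEs in the eCRF". Section 7.22.1.1 defines an AE as a harmful, pathological or unintended change, and its list of what counts includes "Clinically significant abnormalities in physical examination, vital signs, and weight".

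**Infusion-related reactions.** Section 7.22.1.2 requires onset during the infusion or within 24 hours of its start, and that the event "is judged as possibly or probably related to study drug". Table 7-4 in Section 7.22.4 has one category above these two, *Definitely Related*, with the note that "the determination of definitely related can only be used when recurrence of event is observed".

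**Versions.** The document holds two amendments. Section 10 appears only in the Amendment 6 text (10 July 2014); the Amendment 7 text (08 February 2016) breaks off at the start of Section 8. The five-grade scale, the examination rule, the AE definition, the infusion-reaction definition and Table 7-4 stand in both.

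**The concern.** Adverse events by type and severity are the first-listed primary endpoint. Three rules that govern how those events are recorded or displayed disagree with another rule in the same protocol. None is a detail that a protocol leaves to the SAP: each is written down, and so is the rule it conflicts with.

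The device table matters because the protocol itself reports more complications than expected with the first device and introduces a second. A table of device events by severity and relatedness, presented by device, is where a reader would look to compare them. The examination rule matters because Section 10.6.1.1 rests the safety assessment primarily on AE frequency, and two sites reading different sections could code the same finding differently. The infusion-reaction wording matters least, but it is perverse: stronger evidence of causation takes an event out of the definition.

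**Working it through.** No plan figure has to be reproduced. The check compares the categories in each rule with the scale or definition that it should match.

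**1. Severity levels in the device and procedure table**

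| Source | Levels |
|---|---|
| 7.22.3 and Table 7-3, all AEs | mild, moderate, severe, life-threatening, death (5) |
| 10.6.1.1, device and procedure AEs | mild, moderate, severe (3) |

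Grades without a cell: 5 − 3 = 2, namely Grades 4 and 5.

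These grades can apply to device events. The criteria in Appendix 6 give Grade 4 for a local device or prosthesis complication as "Life-threatening; disabling; loss of limb or organ", with death as Grade 5. Appendix 3 lists meningitis, encephalitis and paralysis among expected device effects.

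A programmer following the text has two choices, neither good. Dropping Grade 4 and 5 events makes the severity table disagree with the preferred-term table for the same events. Folding them into the severe row turns it silently into Grade 3 or higher. With at most 12 patients, one affected patient is at least 1/12 = 8.3% of the population, so one misplaced event is visible.

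**2. Examination changes**

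| Finding on examination | Section 7.2 | Section 7.22.1.1 |
|---|---|---|
| Clinically significant worsening | AE | AE |
| New finding without clinical significance | AE | not covered by the examination item |
| Improvement from screening | AE | not an AE |

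The last row is not far-fetched. Section 1.1 describes liver and spleen enlargement in this disease as transient in childhood, and the abdomen is on the Section 7.2 examination list. An enlarged liver at screening that later returns to normal is a change from screening, so Section 7.2 makes it an AE.

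The treatment-emergent summary is limited to events that are new or worsened from baseline, which should keep out a pure improvement. It would not keep out a new but insignificant finding. The by-dose-group summary of patients with any AE carries no such limit.

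**3. Relatedness in the infusion-reaction definition**

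Table 7-4 has four categories, of which 4 − 1 = 3 denote some relation to treatment. The definition names two of the three. *Definitely Related* is missing, although the protocol uses the full range elsewhere: Section 7.24 refers to a "life-threatening (Grade 4) adverse event or death which is considered by the sponsor to be possibly, probably, or definitely related to study drug". Read literally, a reaction classed as *Definitely Related* because it recurred is no longer an infusion-related reaction.

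**The case against.** The strongest reply is that nothing is actually lost, and much of it stands.

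- **Device events.** A reader might infer that the worst device events disappear from the analysis. They do not. The sentence just before the quoted one summarizes device and procedure events by organ class and preferred term with no limit on severity. All treatment-emergent events are summarized by severity and relationship with no three-level restriction. Deaths and serious events are listed separately, and all safety data are listed. What remains is a defect in one cross-tabulation.
- **Stopping rule.** A reader might link the missing grades to the halt in Section 7.24, which acts on Grade 4 events and deaths. The documents do not support that link: the rule works on the sponsor's assessment of events, not on a summary table.
- **Infusion reactions.** A reader might infer that recurrent reactions drop out of a planned count. The Section 10 shown plans no such count, and drug-related treatment-emergent events are summarized separately without excluding *Definitely Related*. Recurrence alone does not earn that category either: Table 7-4 also asks for a fitting time sequence, a known or suspected response pattern and improvement on stopping.
- **Examinations.** A reader might apply the rule to a full examination at every monthly dose. In the Amendment 6 schedule, full examinations are monthly only to Month 54, then at least yearly, with symptom-directed ones in between. Height, weight and head circumference are separate procedures, so measured growth is not clearly caught.

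The conflicts between the written rules survive all of this.

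**Conclusion.** The point holds as three wording defects of unequal weight. The device and procedure severity table cannot show two of five grades. The examination rule contradicts the AE definition and can add non-adverse findings to the AE frequencies. The infusion-reaction definition omits one of three related categories; this is a definitional flaw with no planned table behind it.

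The documents give no event rates, so neither the number of Grade 4 or 5 device events nor the number of surplus examination AEs can be estimated. The conclusion does not depend on them. It is not a finding that severe safety information goes unreported.

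The first part rests on the Amendment 6 wording of Section 10.6.1.1. Whether Amendment 7 kept it cannot be seen. The rules behind the other two parts stand unchanged in Amendment 7.

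**What to change.** 1. In Section 10.6.1.1, tabulate device, surgical-procedure and administration-process AEs by Grades 1 to 5. Check first whether Section 10 of Amendment 7 already does so.
2. In Section 7.2, limit AE capture to clinically significant adverse changes from the screening examination, in line with Section 7.22.1.1. Other changes stay on the examination page of the eCRF, where findings are recorded anyway.
3. In Section 7.22.1.2, define infusion-related reactions as possibly, probably or definitely related, consistent with Table 7-4 and the range used in Section 7.24.

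The cost is three wording edits and one table shell, with no new data collected. If examination changes have already been entered as AEs under the literal wording of Section 7.2, a query to identify them before the final analysis would be needed as well.

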rhHNS, HGT-1410

Name of Inactive Ingredient:

N/A

Names of Devices:

SOPH-A-PORT[®] Mini S, Implantable Access Port, Spinal, Mini Unattached, with
Guidewire (SOPH-A-PORT Mini S)

and

PORT-A-CATH[®] II Low Profile[™] Intrathecal Implantable Access System
(PORT-A-CATH)

Study Title:

An Open-Label Extension of Study HGT-SAN-055 Evaluating Long-Term Safety and
Clinical Outcomes of Intrathecal Administration of rhHNS in Patients with Sanfilippo
Syndrome Type A (MPS IIIA)

Study Number:

HGT-SAN-067

Study Phase: I/II

Device, Intended Use

The SOPH-A-PORT Mini S is a system intended for implantation by physicians. The
SOPH-A-PORT Mini S, once implanted, allows healthcare personnel to administer
HGT-1410 indicated for intrathecal delivery intermittently over a long period of time.

Prior to approval of Amendment 4, patients were implanted with a PORT-A-CATH
(Smith's device). After approval of Amendment 4 all PORT-A-CATH IDDDs requiring
revision or replacement will be replaced with a SOPH-A-PORT at a time judged
appropriate by the Investigator.

Study Objectives:

Primary Objective:

The primary objective of this study is:

- To collect long-term safety and tolerability data in patients with Sanfilippo Syndrome Type A (MPS IIIA) who received HGT-1410 via a surgically implanted intrathecal drug delivery device (IDDD) in study HGT-SAN-055 and elected to continue therapy in study HGT-SAN-067.

Secondary Objectives:

The secondary objectives of this study are:

- To collect as measures of drug efficacy, over an extended treatment period (as change from baseline), the following: clinical, neurological, cognitive, behavioral, functional, and quality of life (QoL) assessments, together with potential imaging and biochemical biomarkers.

Study Endpoints:

Primary Endpoints:

The primary endpoints of this study are related to the long-term safety of intrathecal HGT-1410 administration. The safety endpoints are:

- adverse events (type and severity)
- changes in clinical laboratory testing (serum chemistry including liver function tests, hematology, and urinalysis)
- electrocardiograms (ECG)
- cerebrospinal fluid (CSF) chemistries (including cell counts and inflammatory markers)
- anti-rhHNS antibodies (in CSF and serum).

Secondary Endpoints:

The secondary endpoints of this study are to collect over an extended treatment period (as change from baseline) clinical and potential surrogate biomarker efficacy data:

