6.1.2 Intrathecal Drug Delivery Device

The PORT-A-CATH will continue to be used for the administration of drug product for each patient until such time as an IDDD replacement may be required. Following implementation of protocol Amendment 4, any replacements will be performed using the SOPH-A-PORT Mini S.

After IDDD replacement the drug product will be administered via the SOPH-A-PORT Mini S Implantable Access Port. The SOPH-A-PORT Mini S device is intended for long-term, intermittent access to the IT space for the delivery of investigational drug.

The SOPH-A-PORT Mini S is comprised of the following 7 components:

- One SOPH-A-PORT Mini S Access Port
- One intrathecal port closed-tip catheter
- One guidewire
- Two suture wings
- One 14-gauge Tuohy needle
- One 22-gauge non-coring Huber needle
- One Luer lock Connector.

Further details are provided in the Instructions for Use.

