7.11 Device Data

7.12 Surgical Re-implantation of the IDDD

If a patient's IDDD becomes nonfunctional or infected, it will be replaced or revised so that the patient can remain on study. After full approval of protocol Amendment 4, all IDDD replacements will be made with the SOPH-A-PORT IDDD. If the IDDD device is a PORT-A-CATH IDDD, it will be replaced by a SOPH-A PORT IDDD. Management details for the PORT-A- CATH IDDD or for the SOPH-A PORT IDDD are provided in the respective device's IFU. Procedures for implantation are detailed in the relevant device's Instructions for Use Manual and in the training materials provided by Shire. The patient will be under general anesthesia for this procedure. Standard hospital procedure for surgery will be followed and will include an X-ray to confirm that the device has been (1) surgically implanted correctly, and (2) positioned so that the intrathecal catheter tip is at the mid-thoracic level (a check list is provided in the IDDD Manual).

A post-operative check of the IDDD and incision will be performed on Day 4 following surgery. X-rays may be performed to check placement of the device, as needed, throughout the study (see Section 7.12.1 for limits on the number of x-rays and IDDD revisions and or replacement).

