In another recent study, a patient with MPS VI and spinal cord compression received IT injections of enzyme (Galsulfase) monthly, for 4 months. CSF analysis revealed no inflammatory reaction; no other side effects were noted.¹⁸

Several MPS I patients have been treated since 2005 with IT Laronidase in 2 ongoing clinical trials (clinicaltrials.gov identifiers NCT00215527 and NCT00786968) studying efficacy on spinal cord compression. No results of these trials have yet been published. However, in June 2009 a study further investigating the effectiveness of IT ERT as a treatment for another neurological symptom in MPS I, cognitive decline, was initiated (clinicaltrials.gov identifier NCT00852358).

This study is a 24-month, open label, prospective, randomized trial in 16 patients with MPS I, 6 years of age or older, who have documented evidence of cognitive decline. In this study, the clinical safety of the regimen will be assessed by adverse event (AE) monitoring, CSF laboratory assessments, and clinical evaluations. This study is ongoing; no efficacy or safety data have yet been published as of October 2011.¹⁹

In addition, there are 4 ongoing Shire-sponsored studies that are evaluating IT administration of ERT: A Phase I/II safety and dose escalation study of monthly idursulfase-IT injection for cognitively impaired patients with Hunter syndrome (Study HGT-HIT-045; NCT00920647), the open-label extension to this study (HGT-HIT-046); a Phase I/II ascending dose and dose frequency study of monthly IT injection of HGT-1410 in patients with Sanfilippo Syndrome Type A (Study HGT-SAN-055; NCT01155778), and the open-label extension to this study (HGT-SAN-067; NCT 01299727).

In light of the higher than expected complications experienced with the PORT-A-CATH IDDD, the SOPH-A-PORT Mini S device will be introduced for those patients requiring replacement or revision. This new device has design features anticipated to reduce complications encountered with the PORT-A-CATH IDDD device. Specific device assessments are included in the protocol to collect information with respect to information specific to SOPH-A-PORT Mini S device safety and function.

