6.1.2 Intrathecal Drug Delivery Device

The PORT-A-CATH will continue to be used for the administration of drug product for each patient until such time as an IDDD replacement may be required. Following implementation of protocol Amendment 4, any replacements will be performed using the SOPH-A-PORT Mini S.

After IDDD replacement the drug product will be administered via the SOPH-A-PORT Mini S Implantable Access Port. The SOPH-A-PORT Mini S device is intended for long-term, intermittent access to the IT space for the delivery of investigational drug.

The SOPH-A-PORT Mini S is comprised of the following 7 components:

- One SOPH-A-PORT Mini S Access Port
- One intrathecal port closed-tip catheter
- One guidewire
- Two suture wings
- One 14-gauge Tuohy needle
- One 22-gauge non-coring Huber needle
- One Luer lock Connector.

Further details are provided in the Instructions for Use.

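### Device-related adverse events are to be shown by device, but patient percentages cannot be compared between two ports used in sequence for unequal times

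*Protocol*

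**What the plan says.** Section 10.6.1.1 defines the general adverse event table, for each dose group, as "the number and percentage of patients having any AE, having an AE in system organ class, and having each individual AE". It then turns to the intrathecal drug delivery device (IDDD): "IDDD and procedure-related AEs will be summarized within system organ class by preferred term". It asks for separate tabulations of events related to the device, to device surgery and to the intrathecal administration process, and adds "These summaries will be presented by device and overall, as appropriate". It states no exposure denominator and no rule for assigning an event to a device.

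Other sections fix how the devices are used:

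- Synopsis, Device, Intended Use: "Prior to approval of Amendment 4, patients were implanted with a PORT-A-CATH".
- Section 6.1.2, on the first port: the PORT-A-CATH stays in use "for each patient until such time as an IDDD replacement may be required".
- The same section, on what succeeds it: "Following implementation of protocol Amendment 4, any replacements will be performed using the SOPH-A-PORT Mini S".
- Section 7.12: "After full approval of protocol Amendment 4, all IDDD replacements will be made with the SOPH-A-PORT IDDD".

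Section 10.6.2.1 plans a rate with a 95% confidence interval, and a censored time to first event, for device failures and malfunctions. That section is written in detail for patients with a SOPH-A-PORT.

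The Section 10 wording is that of Amendment 6. Amendment 7 lists the same section in its table of contents, but its text is not in the copy available.

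**The concern.** A percentage of patients compares two devices fairly only if patients are observed on each for similar lengths of time and enter each in a similar way. Neither holds here. PORT-A-CATH time runs from first implant. SOPH-A-PORT time begins after Amendment 4, and for a patient's first SOPH-A-PORT it begins because the earlier port needed revision or replacement. That trigger can itself be counted: under the adverse event definitions in Section 7.22.1, hospital admission to repair or replace a failed device is a serious adverse event.

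Adverse events are a primary endpoint, and Section 1.1 sets an expectation for the new port: "This new device has design features anticipated to reduce complications encountered with the PORT-A-CATH IDDD device". A by-device table of patient percentages would be read against that expectation, yet the figures would partly reflect the order and duration of use rather than the devices.

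**Working it through.** The protocol gives no device event rate and no date for Amendment 4, so there is no figure of its own to reproduce. The check asks what a table of patient percentages shows when both devices carry exactly the same risk.

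**Inputs from the protocol.** All patients start on PORT-A-CATH; replacements after Amendment 4 are SOPH-A-PORT; follow-up T is to Month 78 (Amendment 6) or Month 102 (Amendment 7); at most 12 patients.

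**Assumptions.** Constant hazards, equal on both devices: failures needing replacement λ = 0.01, 0.03 or 0.06 per month; other device events 0.02 per month. Amendment 4 at study month A = 6, 18, 30 or 42. This gives 24 scenarios, with 400,000 simulated patients each. Failures before A are replaced by another PORT-A-CATH; the first failure after A switches the patient to SOPH-A-PORT. The PORT-A-CATH percentage is over all patients and the SOPH-A-PORT percentage is over those who switched.

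**Formulae for failures**, with x = λ(T − A):

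- PORT-A-CATH, at least one failure: 1 − exp(−λT)
- Proportion switching: 1 − exp(−x)
- SOPH-A-PORT, at least one failure among switchers: 1 − x·exp(−x) / (1 − exp(−x))

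**Worked case: T = 78, A = 30, λ = 0.03.** λT = 2.34, so PORT-A-CATH is 1 − 0.096 = 90.4%. x = 0.03 × 48 = 1.44 and exp(−1.44) = 0.2369, so 76.3% switch. SOPH-A-PORT is 1 − 1.44 × 0.2369 / 0.7631 = 55.3%. The simulation gave 90.4%, 76.2% and 55.4%. In 12 patients that is about 11 with a PORT-A-CATH failure (12 × 0.904 = 10.8), against about 5 of 9 on SOPH-A-PORT (12 × 0.762 = 9.1; 9.1 × 0.554 = 5.1), with no true difference.

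**Simulated percentages with at least one event, PORT-A-CATH vs SOPH-A-PORT:**

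| T | A | λ | Failures | Other device events | Mean months on device (SOPH-A-PORT: per switcher) |
|---|---|---|---|---|---|
| 78 | 6 | 0.01 | 54.2 vs 31.7 | 63.6 vs 51.3 | 57.3 vs 40.3 |
| 78 | 30 | 0.03 | 90.4 vs 55.4 | 65.1 vs 42.8 | 55.5 vs 29.6 |
| 78 | 42 | 0.06 | 99.0 vs 71.8 | 66.9 vs 37.2 | 56.7 vs 24.0 |
| 78 | 6 | 0.06 | 99.0 vs 94.2 | 33.3 vs 66.1 | 22.4 vs 56.3 |
| 102 | 18 | 0.03 | 95.3 vs 77.9 | 57.8 vs 65.4 | 48.6 vs 58.0 |
| 102 | 6 | 0.06 | 99.8 vs 98.2 | 33.4 vs 78.4 | 22.6 vs 79.7 |

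**All 24 scenarios.** For failures, SOPH-A-PORT is lower every time, by 1.6 points (99.8 − 98.2; T = 102, A = 6, λ = 0.06) to 45.9 points (90.4 − 44.5; T = 78, A = 42, λ = 0.03). For other device events it is lower in 16 and higher in 8. The sign follows whichever device has more months per patient, and the gap runs from 45.6 points lower (75.9 vs 30.3; T = 78, A = 42, λ = 0.01) to 45.0 points higher (33.4 vs 78.4; last row).

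**Same simulations, events per 100 device-years.** Failures: about 12, 36 or 72 on both devices, matching λ × 1200. Other events: about 24 on both, matching 0.02 × 1200. The largest discrepancy is 0.1, which is simulation error.

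**The case against.** The best reply is that the protocol does not actually fix percentages for the device tables. The percentage sentence is written for dose groups; the device sentences speak only of summarising and tabulating; and Section 10.6.4 leaves final presentations to the SAP, which is not available here. That is correct as far as it goes, and it limits this to an improvement of method. But the split by device is fixed in the protocol, and the one adverse event measure named beside it does not suit that split.

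Second, Section 10.6.2.1 already plans a failure rate and a censored time to first failure. That is a partial answer. It covers failures and malfunctions, and under Section 7.22.1 a malfunction without physiological consequences is not an adverse event, so the event sets differ. It is also detailed for SOPH-A-PORT only. It does not repair the adverse event tables.

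Third, Section 10.1 makes device analyses descriptive, with no testing, and with 12 patients one patient is 8.3 points (100/12). So the smallest gaps above are less than one patient. The larger ones are several patients, and a descriptive table can still mislead.

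Finally, Amendment 7's Section 10 cannot be checked, and its wording may differ.

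**Conclusion.** The point holds as one of non-comparability. If device-related adverse events are shown as crude patient percentages by device, the two columns can differ by up to about 46 points with no difference in risk.

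A reader might infer that the table is bound to favour SOPH-A-PORT. The documents do not support that in general. The direction is settled only for events that trigger the switch. For device events that need not lead to replacement, such as haematoma or pain on injection, it can go either way, and an early Amendment 4, frequent failures or follow-up to Month 102 tends to reverse it. A reader might also infer that every SOPH-A-PORT follows a PORT-A-CATH problem. That is true of each patient's first one; Section 7.12 allows later ones to replace a SOPH-A-PORT.

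The sizes rest on assumed constant hazards, an assumed Amendment 4 date and assumed denominators. The non-comparability itself needs only the sequential, replacement-triggered use that the protocol describes.

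**What to change.** In Section 10.6.1.1, for tables shown by device:

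- Assign each event to the device implanted at onset.
- For IDDD-related events, give the number of events, device-years, and events per device-year with an exact 95% confidence interval.
- For device-surgery events, use the number of procedures as denominator, since these events follow operations rather than time.
- For administration-process events, use the number of administrations by that route, and show lumbar-puncture events separately from either device.
- Keep patient counts as supportive data, labelled as not comparable between devices.

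The cost is wording and some data handling. Sections 7.13.1 and 7.13.4 already put SOPH-A-PORT implant and revision details, and device removals, on the case report form. PORT-A-CATH implant dates must be brought in from HGT-SAN-055, though the treatment-emergent window in Section 10.6.1.1 starts at implant surgery and so already needs them. Intervals will be wide: 12 patients followed from first dose to Month 78 give at most about 78 patient-years (12 × 78/12), and to Month 102 about 102, shared between two devices.
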